#### **4.6 Schedule of Events**

**Table 1: Schedule of Events for Treatment Group**

Study Activity	Baseline	3 Month	6 Month (3 months post-op)	9 Month (6 months post-op)	15 Month (12 months post-op)
Consent	X				
Baseline Questionnaire	X				
Length Assessment	X				
Patient Diary Provided	X				
PTT Experience Questionnaire		X			

Penile Prosthesis Implanted		X			
Penile Prosthesis Length Recorded		X			
PP Follow-Up Questionnaire			X	X	X
Chart Review of Post-Op Complications					X

**Table 2: Schedule of Events for Control Group**

Study Activity	Baseline	3 Month	6 Month	12 Month
Consent	X			
Baseline Questionnaire	X			
Length Assessment	X			
Penile Prosthesis Implanted	X			
Penile Prosthesis Length Recorded	X			
PP Follow-Up Questionnaire		X	X	X
Chart Review of Post-Op Complications				X

## 5 Statistical Plan

### 5.1 Data Handling

All data will be recorded either by the patient themselves or by the provider directly onto printed forms (Attachments). Information will remain de-identified throughout the remainder of the study period and will remain on password protected, Mayo servers.

After completion of the study, de-identified information will be shared with individuals associated with PathRight Medical, Inc. who may assist with portions of the data analysis and/or manuscript drafting. No identifiable information will be sent.

### 5.2 Statistical Analysis

Analyses will be performed using comparisons within patients of same baseline penile stretch length and between groupings of varying lengths. Comparison of device length implanted will be made for subjects using the traction device compared to those who did not utilize traction. Comparisons will also be made on other subjective and objective variables obtained including number of adverse events, complications, subjective responses to questionnaires, or other information. Pre- and post-operative penile lengths will also be compared within individuals. All data will be normalized based on pre-operative stretched penile length.

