## Study Summary

Title	Penile Lengthening Pre-Penile Prosthesis Implantation
IRB Protocol Number	17-011052
Methodology	Open enrollment
Overall Study Duration	3 years
Subject Participation Duration	3 months
Objectives	Compare length of penile prosthesis inserted after traction therapy
Number of Subjects	80
Diagnosis and Main Inclusion Criteria	Men undergoing placement of a penile prosthesis
Study Device	RestoreX®, penile traction therapy
Duration of Exposure	Subjects will use device for 30 minutes, 3 times a day
Reference therapy	Use of the device will be compared against a control group using no traction therapy
Statistical Methodology	Statistical comparisons will be made comparing total length of prosthesis inserted between those using and not using traction, stratified by baseline penile length.

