### **3.4 Consent and Accrual**

During the patient's consultation appointment, they will receive a description of the study and if the patient expresses interest in participating, a formal consent will be reviewed (see **Attachment – Consent Form**).

If the patient successfully completes the consenting process, they will undergo initial study penile length assessments (described later in the protocol). Those wishing additional time to consider participation may be rescheduled to a later date if desired.

At the time of consent, all participants will be assigned a study identifier, with a master list maintained in a password protected database (Mayo server) linking the patient to the identifier. A total of 40 patients will be accrued into each arm of the study, for a total of 80 patients accrued overall. It is estimated that 80 patients will need to be accrued in order to achieve a minimum of 20 subjects in each arm that will complete the study from start to finish.

No limitations will be applied to either clinical site for enrollments, such that it is possible that one clinical site may enroll 100% of the patients.

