### **3.5 Study Schema**

During the initial scheduled clinic appointment, the patient will receive a description of the study, and informed consent. Potential subjects will be notified about the two groups for the study: Treatment (PTT for 30 min 3x/day for 3 months) or No Treatment (control). Subjects planning to have their IPP procedure immediately and do not want to utilize traction therapy will be considered for the control group. Subjects who wish to wait for placement of IPP and are interested in utilizing traction will enter into the treatment group. Those consenting will receive initial study assessments and subjects who take part in the treatment group will be educated on how to use the device properly.

Patients will then be given a baseline questionnaire to complete and, if assigned to the treatment group, begin using the device. Patients in the treatment arm will record a daily journal of their usage of the device.

After 3 months (+1.5 months permitted), patients in the treatment arm will return for their scheduled procedure (control arm patients will undergo surgery without a 3-month delay). Only those who utilized the device for 3 months will be asked to complete a follow-up questionnaire at this time. Patients will also be encouraged to self-report any additional adverse events (AE's) that they encountered over the 3 months of using the therapy.

During surgery, data will be recorded by the surgeon to indicate type, length and approach taken for penile prosthesis implanted as well as any complications of penile prosthesis implantation. These complications may include urethral perforation, corporal perforation, device malfunction, bowel injury or vascular injury; all of which are standard potential complications of the surgery.

Following surgery, patients will be seen in the clinic based on the standard routine clinical practice. During these follow-up appointments, penile length measurements will be performed and recorded.

Patients will also be sent questionnaires by email or by mail (if email not available) at 3, 6, and 12 months post-operatively. If a patient has not returned their questionnaire within 2 weeks, a follow up phone call to the patient will be placed as a reminder. Alternatively, patients may answer the questions over the phone if that method is preferable.

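### Section 5.2 normalises all data on stretched length without naming the operation or fitting it to its own baseline-length comparison; one stated analysis in cm is a cheap improvement

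*Combined protocol and SAP*

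**What the plan says.** Three statements bear on how baseline length enters the primary comparison.

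- Section 5.2, first sentence: "Analyses will be performed using comparisons within patients of same baseline penile stretch length and between groupings of varying lengths". No group width, rounding rule, outcome scale or way of combining groups is given.
- Section 5.2, last sentence: "All data will be normalized based on pre-operative stretched penile length". No operation is named.
- Study Summary: prosthesis length is compared "between those using and not using traction, stratified by baseline penile length". Normalisation is not mentioned.

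The sentence in 5.2 on the primary outcome mentions no baseline length: "Comparison of device length implanted will be made for subjects using the traction device compared to those who did not utilize traction". Penile length itself is covered by "Pre- and post-operative penile lengths will also be compared within individuals", again with no scale.

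Two design features matter. Arms are chosen by the men (section 3.5): "Subjects who wish to wait for placement of IPP and are interested in utilizing traction will enter into the treatment group". On size, section 3.4 says "A total of 40 patients will be accrued into each arm of the study", in order "to achieve a minimum of 20 subjects in each arm that will complete the study from start to finish". The only length assessment scheduled before implantation in Tables 1 and 2 is at baseline, although section 4.5 says only that lengths are taken pre-operatively.

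**The concern.** Normalising on a baseline measurement can mean dividing by it, subtracting it or adjusting for it. For implanted length these are different analyses, with different power and, when the arms differ at baseline, different error rates. The text also plans a comparison within baseline length, and nothing says how the two combine. Several primary analyses are therefore consistent with the plan, and the choice among them could be made after the data are seen.

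Because men choose their arm, baseline length is not balanced by design, so its handling carries more weight than it would in a randomised trial.

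Two smaller ambiguities follow from the same sentence. Pre-operative is not tied to a time before traction; a length taken after traction would contain part of the treatment effect. And applying the rule to all data would take in adverse events, complications and questionnaires, where it has no evident meaning.

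**Working it through.** **The plan's own figure.** 40 accrued and at least 20 completing per arm implies 50% attrition: 20 / (1 − 0.5) = 40 per arm, 80 in total. The arithmetic is consistent. No power, SD, effect or alpha is stated, so there is no power figure to reproduce.

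**Inputs (assumed unless noted).** Stretched length 12 cm, SD 1.5; implant length 20 cm; slope of implant on stretched length 0.4 to 1.0 cm per cm; residual SD 1.2 cm; two-sided 5%. The effect of +0.9 cm is taken from section 1.1, where it is an uncontrolled pilot's change in penile length after implantation. It is an illustration, not a design value for prosthesis length.

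**Regression in cm.** SE ≈ 1.2 × √(2/n).
- n = 20: 0.379 cm; 0.9 / 0.379 = 2.37; power about 64% by the t formula, 62–63% simulated.
- n = 40: 0.268 cm; 0.9 / 0.268 = 3.35; power about 91%.

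**Ratio to stretched length.** To first order, in cm-equivalent units, SD = √[(20/12 − slope)² × 1.5² + 1.2²].
- Slope 0.4: √(1.267² × 2.25 + 1.44) = √5.05 = 2.25 cm.
- Slope 1.0: √(0.667² × 2.25 + 1.44) = √2.44 = 1.56 cm.

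Both exceed 1.2, so the ratio is noisier even with balanced arms. A baseline gap g adds a spurious (20/12 − slope) × g. If the traction arm is 1 cm shorter, that is 0.67 cm (slope 1.0) to 1.27 cm (slope 0.4) in favour of traction. It vanishes only at slope 20/12 = 1.67, that is, strict proportionality.

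**A plain difference** adds (1 − slope) × g: nothing at slope 1.0, 0.6 cm at slope 0.4.

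**Simulated power for +0.9 cm, balanced arms**

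| Analysis | 20 per arm | 40 per arm |
|---|---|---|
| Regression on baseline length | about 62% | 91% |
| 1 cm strata, cm scale | 52–56% | 87–88% |
| 0.5 cm strata | 46–48% | 84–86% |
| Matching to 0.1 cm | 21–23% | 59–61% |
| Pooled ratio | 19–40% | 40–70% |

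Strata lose power partly because some men have no counterpart in the other arm. The share with one at 20 per arm is 92% for 1 cm, 80% for 0.5 cm and 31% for 0.1 cm.

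**Simulated false positives, no true effect**

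| Analysis | 1 cm gap, 20 per arm | 1 cm gap, 40 per arm |
|---|---|---|
| Regression | 5% | 5% |
| 0.5–1 cm strata | 5–6% | 5–6% |
| Pooled difference | 5–23% | 5–43% |
| Pooled ratio | 27–42% | 49–71% |

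With a 0.25 cm gap the ratio gives only 6–8% and 8–10%.

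**Other assumptions.** With implant SD 2 cm, baseline 11 cm (SD 2), effect 1.6 cm and correlation 0.5 at 20 per arm, power is 80.0% for regression, 75.2% for four baseline groups, 59.7% for matching to 0.5 cm and 31.1% for the ratio. If baseline length does not predict implant length, regression gains nothing (68.9% against 70.2% unadjusted).

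**Which length.** Under those second assumptions and a 1.6 cm traction gain in stretched length, adjusting for a post-traction length cuts power from 80.0% to 27.2%, and gives 23.0% false positives when implant length does not differ.

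**What regression leaves.** An unmeasured 0.5 cm arm difference passes through in full: 0.5 / 0.379 = 1.32 and 0.5 / 0.268 = 1.86, or about 25% and 45% false positives at 20 and 40 per arm. With baseline measurement error of SD 0.75 cm and a 1 cm gap, regression gives 5–7% and 6–10%.

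**The case against.** The strongest reply is that the plan already conditions on baseline length. The Study Summary and the first sentence of 5.2 both point that way, and on that reading strata of 0.5 to 1 cm keep false positives at 5–6%. This stands. A reader might infer that the primary analysis will be a pooled ratio with a false-positive rate of 27% or more. The documents do not support that: it needs both the less natural reading and a 1 cm baseline gap, and nothing in them shows that a gap of any given size will occur.

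Second, a reader might take 20 per arm as the primary sample size. Those 20 are men who finish follow-up to 12 months after surgery, whereas implant length is recorded at surgery (section 4.3, Tables 1 and 2). If the plan's accrual and completion figures are met, the number analysed for implant length lies between 20 and 40 per arm. This also stands, and it shrinks the loss.

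Third, a known power loss cannot be shown, because the documents give no SD, slope or correlation. The very low figure for strata needs matching to 0.1 cm, which no section specifies. Well-defined strata are also robust. With a curved relation, unequal arm SDs and a 1 cm gap at 20 per arm, 1 cm strata gave 5.2–5.3% false positives against 6.2–8.0% for linear regression. So regression is not better on every count, and the baseline-length groups deserve to stay in the plan.

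None of this supplies the missing operation, width, scale or combining rule.

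**Conclusion.** The gap is real and worth fixing, as a cheap improvement rather than a fatal flaw. Normalisation is undefined, and no section reconciles it with the comparison by baseline length. Under the natural reading the error rate holds with narrow strata. Against 1 cm strata, regression gains about 6–10 points of power at 20 per arm (62% less 52–56%) and 3–4 at 40 (91% less 87–88%). Against a ratio, which the text leaves open, the gain is about 22–43 points at 20 per arm and 21–51 at 40. The ratio also carries any baseline gap into the result unless implant length is proportional to stretched length.

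Every size here rests on assumed SD, slope and effect. The ranking of regression, strata and ratio was the same under a second set of assumptions. It should not be inferred that one regression resolves the comparison: it covers prosthesis length only, and it adjusts for one measured factor in a trial where men choose their arm.

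**What to change.** In section 5.2, state along these lines:

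> Primary analysis: linear regression of implanted prosthesis length (cm) on arm, with stretched penile length measured at enrolment, before any traction, as a continuous covariate. The adjusted difference is reported with a 95% CI as a non-randomised comparison. No ratio to penile length is used for the primary outcome, and no length measured after traction starts is used as a covariate or divisor. Supportive analysis: the comparison in cm within 1 cm enrolment-length groups, combined over groups, and a description of how it varies between groups. Within-person penile length is analysed as change in cm from enrolment. Adverse events, complications and questionnaires are analysed on their own scales.

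The supportive analysis keeps the comparison within and between length groups that 5.2 already plans. It also serves as the check on linearity, which is preferable to adding a squared term according to its p-value. In the Study Summary, change stratified to adjusted for, and say that the baseline stretched length is pre-traction.

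If the sponsor prefers strata as primary, the minimum is to state the width, the cm scale and the combining rule, accepting the modest power cost given in the verdict.

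Cost: wording, one degree of freedom and a linearity assumption. No new visit is needed, since enrolment length is already scheduled in both arms. There is no gain if baseline length does not predict implant length. Self-selection on unmeasured factors and error in the baseline measurement remain and should be stated as limits.

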## 6 Safety and Adverse Events

### Definition of Adverse Event

Unanticipated Problems Involving Risk to Subjects or Others (UPIRTSO) - any unanticipated problem or adverse event that meets the following three criteria:

Serious: Serious problems or events that results in significant harm, (which may be physical, psychological, financial, social, economic, or legal) or increased risk for the subject or others (including individuals who are not research subjects). These include: (1) death; (2) life threatening adverse experience; (3) hospitalization - inpatient, new, or prolonged; (4) disability/incapacity - persistent or significant; (5) breach of confidentiality and (6) other problems, events, or new information (i.e. publications, interim findings, product labeling change) that in the opinion of the local investigator may adversely affect the rights, safety, or welfare of the subjects or others, or substantially compromise the research data, AND

Unanticipated: (i.e. unexpected) problems or events are those that are not already described as potential risks in the protocol, consent document, not listed in the Investigator's Brochure, or not part of an underlying disease. A problem or event is "unanticipated" when it was unforeseeable at the time of its occurrence. A problem or event is "unanticipated" when it occurs at an increased frequency or at an increased severity than expected, AND

Related: A problem or event is "related" if it is possibly related to the research procedures.

Adverse Event - an untoward or undesirable experience associated with the use of a medical product (i.e. drug, device, biologic) in a patient or research subject.

Serious Adverse Event - adverse events are classified as serious or non-serious. Serious problems/events can be well defined and include:

- Death
- Life threatening adverse experience
- Hospitalization
- Inpatient, new, or prolonged; disability/incapacity
- And/or per protocol may be problems/events that in the opinion of the sponsor-investigator may have adversely affected the rights, safety, or welfare of the subjects or others, or substantially compromised the research data.

All AEs that do not meet any of the criteria for serious, should be regarded as non-serious AEs.

### 6.1 Adverse Event Reporting Period

For the current study, the treatment follow-up period is defined as 3 months following implantation of the penile prosthesis.

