The subject's clinical records will also be reviewed up to 12 months post-operation to check for any complications relating to the surgery including a need for revision surgery, infection or hospitalizations.

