## **6.3 Post-study Adverse Event**

All unresolved AEs will be followed by the study team until the events are resolved, the subject is lost to follow-up, or the AE is otherwise explained. A review of AEs which the subject or subject's physician believe might reasonably be related to participation in the study will be performed up to 12 months following surgery.

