## **6.5 Recording of Adverse Events**

The study team will seek information on adverse events by specific questioning between baseline and the 3 month visit. Information on all adverse events will be recorded immediately in the adverse event section of the specific questionnaire as well as in an adverse event form (see Attachment – Adverse Event Form).

All adverse events occurring during the study period will be recorded. The clinical course will be followed until resolution, stabilization, or until it has been ultimately determined that the study treatment or participation is not the probable cause. Serious adverse events that are still ongoing at the end of the study period will be followed up, to determine the final

outcome. Any serious adverse event that occurs after the study period and is considered to be at least possibly related to the study treatment or study participation will be recorded and reported immediately.

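### Treated men who stop traction or are never implanted have no scheduled adverse-event contact and no defined end of follow-up, and the arms' event counts span unequal windows

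*Combined protocol and SAP*

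**What the plan says.** Section 6.1, headed as the adverse event reporting period, contains one definition: "the treatment follow-up period is defined as 3 months following implantation of the penile prosthesis". Section 6.3 adds that a review of events that "might reasonably be related to participation in the study will be performed up to 12 months following surgery". Sections 3.5 and 4.4 add a record review to 12 months after the operation, aimed at surgical complications.

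Two provisions do not depend on implantation. Section 6.5 says "The study team will seek information on adverse events by specific questioning between baseline and the 3 month visit", and that events in the study period will be recorded. Section 3.5 encourages treated men to report events from the traction months themselves.

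On timing, section 3.5 brings treated men back for surgery at 3 months, with 1.5 more permitted. Controls have surgery without that delay, and Table 2 marks implantation in the baseline column. The questionnaire at the treated man's return is limited by section 3.5 to those who used the device for 3 months.

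On numbers, section 3.4 accrues 40 per arm and says that "80 patients will need to be accrued in order to achieve a minimum of 20 subjects in each arm that will complete the study". Secondary objective 3 evaluates adverse events of the device. Section 5.2 compares the number of adverse events, and gives neither a window nor a denominator.

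**The concern.** The exposure being evaluated for harm ends before the defined follow-up period begins. A man implanted on schedule is covered by the section 6.5 questioning and then by section 6.1. A man who stops traction, cancels surgery or does not return has no implantation date, so neither section 6.1 nor section 6.3 can be applied to him. The section 6.5 questioning also runs to a visit that, for him, was to be the surgery.

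This loss is unlikely to be random. Pain or injury from the device is one reason to stop, so the men least likely to be asked may be those with the most to report. That weakens objective 3.

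A second problem concerns the comparison in section 5.2. A treated man who is implanted is observed through traction and then after surgery, and a control essentially only after surgery. A raw count of events would then differ between arms even if the device did nothing.

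**Working it through.** **1. The plan's own allowance.** Inputs from section 3.4: 40 accrued and at least 20 completing in each arm. Implied non-completion is 1 − 20/40 = 0.50. Checking back: 20 / (1 − 0.50) = 40 per arm, and 2 × 40 = 80 in total, as stated. The allowance applies to both arms and to the whole course, including the 12-month questionnaires. It is not split by stage or reason.

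**2. Windows in months from baseline.** Inputs: surgery at 3 to 4.5 (treated) or about 0 (control); 3 months after implantation (6.1); 12 months after surgery (6.3).

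| Man | Implanted | 6.1 period ends | 6.3 review ends |
|---|---|---|---|
| Treated, earliest | 3 | 3 + 3 = 6 | 3 + 12 = 15 |
| Treated, latest | 4.5 | 4.5 + 3 = 7.5 | 4.5 + 12 = 16.5 |
| Control | about 0 | 3 | 12 |
| Treated, never implanted | none | undefined | undefined |

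**3. Contacts for a treated man who is not implanted.**
- Table 1 lists nothing between baseline and month 3, and has no adverse-event row.
- The month-3 column holds the traction questionnaire and the implantation. Section 3.5 places both at the return for surgery.
- A man who stopped early is outside the questionnaire group. A man who finished traction but declined surgery is inside it, but has no scheduled occasion to receive it.
- The later questionnaires are timed in months after the operation, so they have no date for him.
- Section 6.5 relies on a study period that is not defined. The Study Summary gives participation as 3 months, section 1.5 allows up to 1 year of follow-up, and section 6.1 gives 3 months after implantation.
- The 3 month visit itself differs by arm: the surgical return in Table 1, a post-operative questionnaire point in Table 2.

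**4. How many men.** The number never implanted lies between 0 and 20 of 40. Taking 0, 5, 10 and 20 as an assumed range gives 0%, 12.5%, 25% and 50% of the arm. The top value needs every allowed non-completer to be lost before surgery.

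**5. Unequal observation in section 5.2.** If sections 6.5 and 6.1 are read together, an implanted treated man is observed for 6 to 7.5 months and a control for about 3. The ratios are 6/3 = 2 and 7.5/3 = 2.5. If events unrelated to device or surgery arose at a constant rate (an assumption), the treated arm would record 2 to 2.5 times as many such events per man with no device effect. The 3 months after implantation are the window that both arms share.

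**The case against.** The strongest reply is that the plan does capture harm before implantation. Section 6.5 requires specific questioning from baseline and recording of all events, section 3.5 adds self-report, section 6.3 follows unresolved events without any surgery condition, and section 6.5 also covers possibly related serious events after the study period. Section 6.1 can be read as fixing only when follow-up ends for implanted men. This stands against the reading that non-implanted men have no harm window at all, which a reader might infer from section 6.1 alone. It does not supply a contact or an end date for a man who never returns, and following up an unresolved event presupposes that someone has learned of it.

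Four other strong readings also fail.
- **Half the treated arm lost, and almost no controls.** The allowance in section 3.4 is the same for both arms and covers every stage. A man lost nine months after implantation is a non-completer with a full section 6.1 period.
- **A large calculated share of missed events.** With a fraction f not implanted and an event rate k times that of implanted men, the share arising in non-implanted men is fk / ((1 − f) + fk). Assuming f from 0.10 to 0.50 and k from 1 to 3, it runs from 10% (f = 0.10, k = 1) to 75% (f = 0.50, k = 3). As a share missed, that assumes nothing is captured by sections 3.5 and 6.5. If half were captured, f = 0.10 would give 5% to 12.5%. The documents support no particular value.
- **The record review as a lost device-harm window.** Sections 3.5 and 4.4 aim it at complications of surgery, so tying it to surgery is reasonable.
- **A weakened halting rule.** Section 6.6.2 counts serious events with no implantation condition. It depends on events being reported, but an effect on it is speculative.

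**Conclusion.** The point holds as a gap in follow-up for a defined group, together with an unequal comparison. Sections 6.1 and 6.5 do not agree on when adverse events are collected. For treated men who stop traction or are never implanted, no adverse-event contact is scheduled and no end of follow-up is set. That the missed events would tend to be those that caused stopping is a judgement about mechanism; the documents give no data on it. The number of men is unknown, with 20 of 40 as a ceiling and no basis for a central estimate.

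The net direction of bias in section 5.2 cannot be stated. A reader might infer that treated-arm harm is simply understated. Missed events in men who stop would lower the treated count, but the longer observation of implanted treated men (about 6 to 7.5 months against about 3) would raise it. The window lengths assume that control surgery takes place at about baseline, as Table 2 marks it. Because both problems bear on objective 3 and can be settled by a few definitions, the plan should be changed.

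**What to change.** - **Section 6.1:** start the reporting period at consent in both arms. End it 3 months after implantation or, for a man not implanted, at a fixed time from consent, for example 7.5 months (the latest permitted surgery at 4.5 plus 3). Define the study period in these terms, and reconcile section 6.5 with it, including what the 3 month visit means in each arm.
- **Sections 6.5 and 3.5:** put the adverse-event questions to every man issued the device, whether or not he returns for surgery, by the phone or mail route already used for the surveys.
- **Section 6.3:** give the related-event review an end date for men not implanted. The matching time would be 15 to 16.5 months from consent.
- **Section 5.2:** report device events with all men issued the device as the denominator, show events before and after implantation separately, and compare arms only on the 3 months after implantation.

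The cost is protocol wording and some extra phone contacts, for at most about 20 men if the whole allowance were lost before surgery. No new visit is needed. The reported device-event rate may be less favourable than it would otherwise have been.
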